2.1.3.1 Primary efficacy endpoint(s)

The primary efficacy variable is the change in HbA1c from baseline (scheduled day 1) to Week 24 which is defined as: HbA1c value at Week 24 – HbA1c value at baseline (%).

Results for primary efficacy endpoint will also be presented in mmol/mol.

2.1.3.2 Secondary efficacy endpoint(s)

Secondary efficacy endpoints are:

- Change in HbA1c (mmol/mol and %) from baseline to Week 12,
- Change in FPG (mmol/l and mg/dL) from baseline to Week 12 and Week 24,
- Change in fasting SMPG (mmol/l and mg/dL) from baseline to Week 12 and Week 24,
- Change in 4-point SMPG (mmol/l and mg/dL) profiles per time-point from baseline to Week 4, Week 8, Week 12 and Week 24,
- Change in 8-point SMPG profiles per time-point from baseline to Week 12 and Week 24,
- Change of mean 24-hour plasma glucose based on 8-point SMPG (mmol/l and mg/dL) from baseline to Week 12 and Week 24,
- Change in variability of fasting SMPG from baseline to Week 12 and Week 24,
- Change in variability of 24-hour plasma glucose based on 8-point SMPG (mmol/l and mg/dL) from baseline to Week 12 and Week 24,
- Percentage (%) of patients reaching target HbA1c <7% and ≤6.5% at Week 12 and Week 24
- Percentage (%) of patients reaching target HbA1c <7% at Week 24 without severe and/or confirmed hypoglycemia (≤70 mg/dL) during the 24 weeks treatment period,
- Percentage (%) of patients reaching target HbA1c <7% at Week 24 without severe and/or confirmed hypoglycemia (<54 mg/dL) during the 24 weeks treatment period,
- Percentage (%) of patients reaching target HbA1c <7% at Week 12 without severe and/or confirmed hypoglycemia (≤70 mg/dL) during the 12 weeks treatment period,
- Percentage (%) of patients reaching target HbA1c <7% at Week 12 without severe and/or confirmed hypoglycemia (<54 mg/dL) during the 12 weeks treatment period,
- Percentage (%) of patients reaching target HbA1c ≤6.5% at Week 24 without severe and/or confirmed hypoglycemia (≤70 mg/dL) during the 24 weeks treatment period,
- Percentage (%) of patients reaching target HbA1c ≤6.5% at Week 24 without severe and/or confirmed hypoglycemia (<54 mg/dL) during the 24 weeks treatment period,
- Percentage (%) of patients reaching target HbA1c ≤6.5% at Week 12 without severe and/or confirmed hypoglycemia (≤70 mg/dL) during the 12 weeks treatment period,

- Percentage (%) of patients reaching target HbA1c ≤6.5% at Week 12 without severe and/or confirmed hypoglycemia (<54 mg/dL) during the 12 weeks treatment period,
- Percentage (%) of patients with SU or meglitinide dose reduction/discontinuation due to hypoglycemia over 24 weeks of treatment,
- Percentage of patients requiring rescue therapy during 24 weeks treatment period.

Any technical details related to computation and imputation for missing data are described in section 2.5.

2.1.4 Safety endpoints

The safety analysis will be based on:

- All hypoglycemia events (according to American Diabetes Association [ADA] Workgroup on Hypoglycemia),
- Local tolerability at injection site,
- Hypersensitivity reactions,
- Adverse events with special interest (AESI) with immediate notification:
 - Increase in alanine aminotransferases (ALT);
 - Pregnancy;
 - Symptomatic overdose with IMP/NIMP;
- Other adverse events (AE) or serious adverse events (SAEs),
- Vital signs including body weight.

In case of premature permanent IMP discontinuation or rescue therapy intake, the process described in Section 2.5.4 will be applied to retrieve safety assessments performed at the end of treatment visit or at pre-rescue visit.

Observation period for safety endpoints

The observation period of safety data will be divided into 3 segments:

• **The pre-treatment period** is defined as the time between the date of the signed informed consent and the first injection of open-label IMP.

- The on-treatment period (24-week on-treatment period / 24-week TEAE period) is defined as the time from the first injection of open-label IMP up to 7 days (or 2 days for hypoglycemia) after the last injection of open-label IMP, regardless of the introduction of rescue therapy. The 7-day interval is chosen based on the half-life of the IMP (approximately 5 times the half-life of Tresiba).
 - **12-week on-treatment period (12-week TEAE period)** is defined as the time from the first injection of IMP up to Week 12 or 7 days (or 2 days for hypoglycemia) after the last injection of IMP whichever comes earlier.
- **The post-treatment period** is defined as the time starting 8 days (or 3 days for hypoglycemia) after the last injection of open-label IMP (after on-treatment period). The baseline value for safety endpoints will be the last available value prior to the first injection of open-label IMP.

The on-study observation period is defined as the time from start of treatment until the end of the study (defined as last protocol planned visit or the resolution/stabilization of all serious adverse events and adverse events with pre-specified monitoring).

The baseline value for safety endpoints will be the last available value prior to the first injection of open-label IMP.

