#### **Observation period of efficacy endpoints**

The 24-week on-treatment period for efficacy endpoints (primary and secondary efficacy endpoints) is defined as the time from the first injection of open-label IMP up to 7 days after date of last IMP administration for HbA1c, 0 day for 4-point and 8-point SMPG and insulin dose, 1 day for FPG and fasting SMPG, 2 days for hypoglycemia after the last injection of open-label IMP or up to the introduction of rescue therapy, whichever is the earliest.

The randomized 24–week period for efficacy variables is defined from first dose of IMP up to Week 24, regardless of study treatment discontinuation and intake of rescue therapy.

The baseline value for efficacy endpoints is the last available value prior to the first injection of open-label IMP.

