#### 10.1.3 Post-treatment follow-up phone call visit (V21)

Following the last injection of insulin Toujeo or the Tresiba either as scheduled or prematurely, a post-treatment follow-up phone call visit is performed 7 (-1/+3) days after the end of treatment visit for patients who completed the study or withdrew from the study at the time of the open-label IMP discontinuation. The post-treatment follow-up phone call visit is not performed for patients who prematurely discontinued the open-label IMP treatment and stay in the study up to completion. This visit can be a phone call visit or an on-site visit in case of ongoing or new AE during the post-treatment period, if necessary.

The patient is called by the investigator or medically qualified designee at certain, previously agreed time point.

During the phone call, the following questions are to be asked:

- Did you experience any new medical event, disease or symptom since the last visit?
- Did you experience any changes in a pre-existing medical condition, disease or symptom since the last visit?
- Did you change, take or add any new medications since the last visit?
- Did you experience any events or symptoms of hypoglycemia?

All reports of hypoglycemic events (if any) or any adverse events are recorded. The use or change of any concomitant medications, including rescue therapy, is recorded.

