Hypoglycemia will be determined during the 12-week on-treatment period and the 24-week on-treatment period, respectively (used for Safety endpoint, as defined in Section 11.4.3.1)

Patients who initiate recue therapy during the 12-week on-treatment period or during the 24-week on treatment period, respectively, will be considered as failure for this given period.

Patients with missing HbA1c at a given visit will be considered as failure for this given visit.

The 24-week on treatment period as defined for Safety endpoint will be used (refers to Section 9.2.2.

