### 11.4.3 Analyses of safety data

### 11.4.3.1 Observation period of safety endpoints:

The observation period of safety data will be divided into 3 segments:

- The **pre-treatment period** is defined as the time between the date of signed informed consent and the first injection of open-label IMP
- The **on-treatment period** (24-week on-treatment period) is defined as the time from the first injection of open-label IMP up to 7 days after the last injection of open-label IMP, regardless of the introduction of rescue therapy. The 7-day interval is chosen based on the half-life of the IMP (approximately 5 times the half-life of Tresiba),

- 12-week on-treatment period is defined as the time from the first injection of IMP up to Week 12 or 7 days after the last injection of IMP whichever comes earlier.

• The **post-treatment period** is defined as the time starting 8 days after the last injection of open-label IMP (after on-treatment period).

The baseline value for safety endpoints will be the last available value prior to the first injection of open-label IMP.

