1.5 MODIFICATIONS TO THE STATISTICAL SECTION OF THE PROTOCOL

The statistical section of the protocol was never changed in an amendment.

The protocol history table below gives the timing, rationale and key details of major changes to the protocol statistical section.

Amendment Number	Date Approved	Rationale	Description of statistical changes
NA	NA	Modification of basal insulin dose (U and U/kg body weight) analysis	MMRM analysis for the change from baseline to Week 12 and Week 24 of basal insulin dose will be replaced by a descriptive analysis.
NA	NA	Modification of basal insulin doses section	Basal insulin dose was included in the Section 2.4.3.1
NA	NA	Modification of analysis in 8-point SMPG profiles per time-point	MMRM analysis for the change in 8-point SMPG profiles per time-point from baseline to Week 12 and Week 24 was removed. Only a descriptive analysis will be performed.
NA	NA	Modification of analysis in 4-point SMPG profiles per time-point	MMRM analysis for the change in 4-point SMPG profiles per time-point from baseline to Week 12 and Week 24 was removed. Only a descriptive analysis will be performed.

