2.4.5.1 Analyses of hypoglycemia

All safety analyses of hypoglycemia events will be performed by treatment group in the safety population on events occurring during the TEAE period (as described in Section 2.1.4):

- Percentage (%) of patients with at least one hypoglycemia event will be presented for any hypoglycemia and for each hypoglycemia category of time: any time, nocturnal, daytime (as described in Section 2.1.4.1). The Odds Ratio and its corresponding 95% CI of Toujeo arm over Tresiba arm for each hypoglycemic event will be estimated by a logistic regression model using the same approach as the one described for categorical efficacy endpoint.
- Percentage (%) of patients with at least one hypoglycemia event will be presented for any hypoglycemia and for each hypoglycemia category of time: any time, nocturnal, daytime (as described in Section 2.1.4.1), excluding hypoglycemia occurring after the initiation of rescue therapy.
- Percentage (%) of patients with at least one hypoglycemia event, will be presented by study period (for ≤12 weeks, for >12 weeks to ≤24 weeks and during 24 weeks treatment period) for any hypoglycemia and for each hypoglycemia category (as described in Section 2.1.4.1). The Odds Ratio and its corresponding 95% CI of Toujeo arm over Tresiba arm for each hypoglycemic event will be estimated by a logistic regression model using the same approach as the one described for categorical efficacy endpoint.
- Percentage (%) of patients with at least one hypoglycemia event, will be presented by study period (for ≤12 weeks, for >12 weeks to ≤24 weeks and during 24 weeks treatment period) for any hypoglycemia and for each hypoglycemia category (as described in Section 2.1.4.1) excluding hypoglycemia occurring after the initiation of rescue therapy.
- Percentage (%) of patients with at least one severe hypoglycemia event will be summarized by symptom during 24 weeks treatment period),

- Number and rate of hypoglycemia event per patient-year will be summarized for any hypoglycemia and for each hypoglycemia category (as described in Section 2.1.4.1). For each hypoglycemic event ,the rate ratio, and its corresponding 95% CI, of Toujeo arm over Tresiba arm will be estimated using an over-dispersed Poisson regression model adjusted on randomization strata of screening HbA1c (<8.0%, ≥8.0%) and randomization strata of SU or meglitinides at screening (Yes vs No),

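### The SAP cuts the safety-analysis window for hypoglycemia from 7 to 2 days after the last injection, unlisted and unexplained, so day 3–7 events recorded only on the hypoglycemia page enter no planned hypoglycemia analysis

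*SAP*

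**What the plan says.** **Protocol, safety.** Sections 9.2.2 and 11.4.3.1 define a single on-treatment period for safety data, running "up to 7 days after the last injection of open-label IMP, regardless of the introduction of rescue therapy". The stated reason is: "The 7-day interval is chosen based on the half-life of the IMP (approximately 5 times the half-life of Tresiba"). Section 9.2.2 lists hypoglycemia among the safety endpoints, and 11.4.3.2.1 analyses it during the on-treatment period. No shorter rule for hypoglycemia appears in any of these places.

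**Protocol, efficacy.** The 2-day value appears once, in the observation period for efficacy endpoints under 9.2.1: "2 days for hypoglycemia after the last injection of open-label IMP or up to the introduction of rescue therapy". For the composites that combine an HbA1c target with absence of hypoglycemia, however, 11.4.2.2 takes hypoglycemia from the period "used for Safety endpoint, as defined in Section 11.4.3.1", which is the 7-day one.

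**SAP.** Section 2.1.4 sets the safety period "up to 7 days (or 2 days for hypoglycemia) after the last injection of open-label IMP", does the same for the 12-week period, and starts the post-treatment period for hypoglycemia on day 3. It repeats the half-life reason for 7 days and offers none for 2. Section 2.4.4.2.1 ties the composites to the efficacy period of 2.1.3. Section 2.1.4.1 defines a post-treatment category of hypoglycemia, but 2.4.5.1 states: "All safety analyses of hypoglycemia events will be performed by treatment group in the safety population on events occurring during the TEAE period".

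**Record of changes.** SAP 1.5 has a table that "gives the timing, rationale and key details of major changes to the protocol statistical section". Its four rows concern basal insulin dose (two) and the 8-point and 4-point SMPG profiles (one each). SAP 1.6 reports no SAP amendment.

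**Collection.** At the follow-up call (V21, Protocol 10.1.3) patients are asked: "Did you experience any events or symptoms of hypoglycemia"?

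**The concern.** The introduction to the protocol singles out hypoglycemia as the comparison of special interest in this head-to-head trial, so the rule for which events count should be the protocol's own or an openly declared departure from it. Here the counting period changes between the documents, with no reason given and no entry in the table meant for such changes. The listed changes include one that merely places basal insulin dose in another section of the SAP.

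Two practical consequences follow. First, events on days 3 to 7 after the last injection are assigned to a category that is defined and then never analysed. Second, the same event can be classified in two ways. Hypoglycemia that meets SAE criteria also goes on the AE and SAE forms (Protocol 10.6.1), where the window remains 7 days. Such an event on day 5 would be a treatment-emergent SAE in one table and post-treatment hypoglycemia under SAP 2.1.4.1.

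**Working it through.** **1. The two documents side by side**

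| Item | Protocol | SAP |
|---|---|---|
| Safety window, hypoglycemia | last injection + 7 days (9.2.2, 11.4.3.1) | last injection + 2 days (2.1.4) |
| Safety window, other AEs | last injection + 7 days | last injection + 7 days (2.1.4) |
| Hypoglycemia in the composites | safety period, 7 days (11.4.2.2) | efficacy period, 2 days (2.4.4.2.1, 2.1.3) |
| Hypoglycemia, days 3–7 | on-treatment, analysed (11.4.3.2.1) | post-treatment category (2.1.4.1), no table or listing (2.4.5.1) |
| Listed as a change | – | neither change is in SAP 1.5 |

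**2. Which events drop out.** Hypoglycemia is recorded on its own page of the case report form (Protocol 10.4.4, note to Table 3, and 10.6.1). Only events that meet SAE criteria are also entered as AEs. The post-treatment AE tables in SAP 2.4.5.2 therefore do not pick up the rest. Under Protocol 10.6.1, severe hypoglycemia is an SAE only if it meets SAE criteria, so the rest can include severe events.

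**3. Share of the window.** The difference is 7 − 2 = 5 days.

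- 24-week completer (168 days treated): protocol window 168 + 7 = 175 days, SAP window 168 + 2 = 170 days. Share removed: 5/175 = 2.9%.
- Illustrative stop after 84 days: 5/(84 + 7) = 5/91 = 5.5%.
- Illustrative stop on Day 28: 5/(28 + 7) = 5/35 = 14.3%.
- Upper limit over all 920 patients: 920 × 5/365.25 = 12.6 patient-years, or 6.3 per arm.

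These are shares of days. The documents give no expected event counts for this period.

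**4. The plan's own reason for 7 days.** Taking 7 days as 5 half-lives implies 168 h/5 = 33.6 h, so 48 h is 48/33.6 = 1.43 half-lives. If decay is simply exponential (an assumption), 2^(−1.43) = 37% of the drug remains at 48 h, against 2^(−5) = 3% at 7 days. This shows that the retained reason does not explain the 2-day value. It measures residual drug, not risk of hypoglycemia.

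**5. Denominator.** Rates divide by days of exposure (SAP 2.5.1), and exposure ends at the last dose (SAP 2.4.3.2). For a 168-day completer, a 7-day tail adds 7/168 = 4.2% of event time with no matching denominator, and a 2-day tail adds 2/168 = 1.2%.

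**6. Sample size.** This does not depend on the window. The planned figure reproduces: 2 × (1.960 + 1.282)² × 1.4²/0.3² gives 458 per arm, against 460 planned.

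**The case against.** A case can be made for 2 days. It is the only hypoglycemia-specific window in the protocol, which is itself uneven: it sets 2 days for hypoglycemia in efficacy endpoints and then sends the composites to the safety period. The SAP applies one value throughout. After IMP stops, any treatment is permitted (Protocol 8.9), so later events may reflect a successor therapy, and a longer tail adds events without exposure days. All of this stands. It is a reason to state and justify 2 days, not to adopt it without comment.

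The proposed extra count also has limits. In the flow chart, completers' diaries are collected and SMPG ends at V20. V21 is a telephone call 6 to 10 days after that visit. Day 3–7 events in completers therefore rest largely on recall, often without a glucose value, while the main categories require one.

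A reader might infer four stronger points that the documents do not support:

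- *That these events appear in no analysis at all.* Those meeting SAE criteria reach the AE and SAE tables and the SAE listing.
- *That follow-up is shortened.* Collection is unchanged; only the analysis window moves.
- *That early stoppers lose follow-up.* They are to stay in the study to its scheduled end (Protocol 10.3.4). Those who stay do not receive the V21 call, so their events come from continued study visits.
- *That the cut favours one arm.* The protocol's introduction gives activity up to 36 hours for Toujeo and beyond 42 hours for Tresiba. The second figure comes from clamp studies in type 1 diabetes and is open-ended. Neither describes what happens after 48 hours.

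**Conclusion.** The discrepancy is real and undocumented. The safety-analysis window for hypoglycemia goes from 7 days to 2, and the composites move from the safety period to the efficacy period. Neither change is explained or listed. Day 3–7 events held only on the hypoglycemia page are left out of every planned hypoglycemia analysis, and an SAE-level event on those days is classified in two ways.

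The numerical effect is likely small. It touches at most 2.9% of a 24-week completer's window, and a larger share only for early stoppers (14% in the Day-28 illustration). It applies to both arms, and the safety analyses are mainly descriptive. No between-arm bias is shown, and the HbA1c conclusion does not depend on it. The judgement that the effect is small assumes that events are not concentrated in days 3 to 7, which the documents neither show nor exclude. The proposed count would settle that, within the limits of recall. Whether 2 or 7 days is the better main window is open to argument; leaving the choice undeclared and the remainder unreported is not.

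**What to change.** 1. Reconcile Protocol 11.4.3.1 with SAP 2.1.4 (safety window) and Protocol 11.4.2.2 with SAP 2.4.4.2.1 (composites).
2. Add both changes to the table in SAP 1.5, each with its reason.
3. If 2 days stays as the main window, add to SAP 2.4.5.1 a by-arm count of patients and events on days 3 to 7 after the last injection, or a 7-day sensitivity analysis. Split it by whether another insulin had been started. This gives the post-treatment category in SAP 2.1.4.1 an output and makes any double classification of an SAE visible.
4. If 7 days is used for rates, count the matching days in the denominator.

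The cost is SAP wording and one extra table, with no new visit and no change to the sample size or the primary analysis. The table should carry a note that completers' day 3–7 events rest largely on recall at V21 and may reflect successor therapy.

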2.1.4.1 Hypoglycemia events

All hypoglycemia events will be categorized as follows according to ADA category (1):

- Severe hypoglycemia: an event requiring assistance of another person to actively administer carbohydrate, glucagon, or other resuscitative actions. Severe hypoglycemia will be qualified as an SAE only if it fulfills SAE criteria. All events of seizure, unconsciousness or coma must be reported as SAEs;
- Documented symptomatic hypoglycemia: an event during which typical symptoms of hypoglycemia are accompanied by a measured plasma glucose concentration of ≤70 mg/dL (3.9 mmol/L);
- Asymptomatic hypoglycemia: an event not accompanied by typical symptoms of hypoglycemia but with a measured plasma glucose concentration ≤70 mg/dL (3.9 mmol/L);
- Severe and/or confirmed hypoglycemia by a plasma glucose concentration ≤70 mg/dL (3.9 mmol/L): any hypoglycemia event of the three above categories;
- Probable symptomatic hypoglycemia: an event during which symptoms typical of hypoglycemia are not accompanied by a plasma glucose determination, but was presumably caused by a plasma glucose concentration ≤70 mg/dL (3.9 mmol/L); symptoms treated with oral carbohydrate without a test of plasma glucose;

• Pseudo-hypoglycemia: an event during which the person with diabetes reports any of the typical symptoms of hypoglycemia with a measured plasma glucose concentration >70 mg/dL (>3.9 mmol/L) but approaching that level.

Hypoglycemia observation periods

- **Pre-treatment hypoglycemia events** are events that occur during the pre-treatment period,
- **Treatment-emergent hypoglycemia events** are events that occur during the 24 Week on-treatment period,
 - **12 week Treatment-emergent hypoglycemia events** are events that occur during the 12weeks on-treatment period;
- **Post-treatment hypoglycemia events** are events that occur during the post-treatment period.

Hypoglycemia events will be evaluated regardless of the time of onset and in the following time periods defined by time of the day:

- Daytime hypoglycemia: any hypoglycemia of the above categories that occurs:
 - Between 06:00 and 23:59.
- Nocturnal hypoglycemia: any hypoglycemia of the above categories that occurs:
 - Between 00:00 and 05:59 am, regardless whether patient was awake or woke up because of the event.
 - Between 00:00 and 7:59 am, regardless whether patient was awake or woke up because of the event.
 - Sleep status: patient was asleep between bedtime and before getting up in the morning, ie, before the morning determination of fasting pre-breakfast SMPG and patient woke-up due to the hypoglycemia.
- At any time of the day distributed by 2-hour of the day (0:00-23:59).

In addition of the threshold of \leq 70 mg/dL (3.9 mmol/L), hypoglycemia episodes with plasma glucose <54 mg/dL (3.0 mmol/L) will be analysed.

